9.1.1.3 Site(s) Performing Correlative Study

The correlative studies will be performed at Yale Cancer Center ([name] lab) and [name] [name]'s lab at Vanderbilt University as described above in 9.1 and in [Appendix J](#).

9.1.2 Evaluate whether PD-L1 expression in CD34+ blasts from human MDS BM correlates with the response to anti-PD1 therapy

9.1.2.1 Collection and Handling of Specimens

BM aspirate and blood collected in EDTA tubes and clot sections in 10% formaldehyde will be as described above. We will separate mononuclear cells from BM aspirate and blood in EDTA as described at Appendix D. Samples will be used for experiments and samples leftover will be stored in liquid nitrogen and should be clearly marked with the patient's identification number (given at the time of registration), study number, sample collection date, and sample source (blood or BM).

Formalin-fixed paraffin-embed clot section will be cut at maximum 3 mm thickness

9.1.2.2 Shipping of Specimen(s)

Fresh BM aspirate and blood samples will be collected at Yale and other participating sites to deliver overnight and will be processed (according to [Appendix D](#)) at the Hematology Tissue Bank at Yale University. Upon request of the Study Chair they will be batch shipped to Yale Cancer Center. Samples will be shipped or delivered to the Hematology Tissue Bank: [name]. [contact]

Formalin-fixed paraffin-embed block of clot section from external sites should be delivered to Hematology Tissue Bank at Yale University, or if the sample is from a Yale patient, it will be stored in the Yale Pathology repository until ready for further processing.. Sections will be cut at maximum 3 mm thickness at Research Histology lab at Yale University.

9.1.2.3 Site(s) Performing Correlative Study

All correlative studies will be performed at Yale Cancer Center [name]'s lab) and [name] [name]'s lab at Vanderbilt University as described above and in [Appendix J](#).

9.1.3 Characterize functional dynamics of immune cell subsets in MDS patients pre- and post- anti-PD1 therapy

9.1.3.1 Collection and Handling of Specimens

BM aspirate and blood collected in EDTA tubes will be as described above. We will separate mononuclear cells from BM aspirate in EDTA as described at [Appendix D](#). Samples will be used for experiments and samples leftover will be stored in liquid nitrogen and should be clearly marked with the patient's identification number (given at the time of registration), study number, sample collection date, and sample source (or bone marrow).

9.1.3.2 Shipping of Specimen(s)

Fresh BM aspirate and blood samples will be collected at Yale and other participating sites to deliver overnight and will be processed (according to [Appendix D](#)) at the Hematology Tissue Bank at Yale University. Upon request of the Study Chair they will be batch shipped to Yale Cancer Center. Samples will be shipped or delivered to the Hematology Tissue Bank: [name]. [contact].

9.1.3.3 Site(s) Performing Correlative Study

All correlative studies will be performed at Yale Cancer Center [name]'s lab) and [name] [name]'s lab at Vanderbilt University as described above and in [Appendix J](#).

9.2 Special Studies: N/A

10. STUDY CALENDAR

Baseline evaluations are to be conducted within 2 weeks prior to start of protocol therapy. In the event that the patient's condition is deteriorating, laboratory evaluations should be repeated within 48 hours prior to initiation of the next cycle of therapy. An interim history and physical to evaluate signs and symptoms of autoimmune events should be done with each visit and prior to each infusion. An autoimmune check list will be used. Interim history, evaluation, and laboratory assessments will be performed before Administration of entinostat. Patients will have weekly blood test (Complete blood counts (CBC)) throughout the study at the clinic. CBC with differentials, serum chemistry and Liver function tests (LFTs) will be performed at least every 2 weeks.

Procedure	Screening# ≤ 14 days from Baseline (First day study drug administra- tion)	Each Cycle (21 days)				Discontinuation of Study Drug or progression	Monthly after removal from study for any reason for 6 months
		D1 +/- 1	D8 +/- 1	D15 +/- 1	D17-D20		
Entinostat (depending on dose level)		X	X	X			
Pembrolizumab (MK-3475)		X (Starting in C2)					
Age, gender, height, baseline medications, record prior therapy, informed consent , EKG	X						
Record prior anti-cancer therapies	X						
Physical examination, performance status, vital signs, weight	X	X				X	
ECOG performance status	X	X					X
Hematology ¹	X	X	X	X			X
Serum chemistry ²	X	X	X	X			X
Reticulocyte count	X	X					
Pregnancy testing ³	X						
Record adverse events ⁴		X		X			X

Record concomitant medications/ procedures		X				X	
Bone marrow aspirate and biopsy and peripheral blood for disease assessment and correlative studies ⁵	X				X (of first cycle, and then every 2 cycles [C3, 5, etc])	X	
TSH	X			X			
Survival Follow-up ⁶							X

Cycle1: Entinostat 8mg po on D1, 8 and 15, no Pembrolizumab (MK-3475)

DL1: Entinostat 8mg on D1, 8 of 21-day cycles, Pembrolizumab (MK-3475) 200mg IV over 30 mins on D1 of 21-day cycles

DL2: Entinostat 8mg on D1, 8, 15 of 21-day cycles, Pembrolizumab (MK-3475) 200mg IV over 30 mins on D1 of 21-day cycles

DL-1: 8mg on D1 of 21-day cycles, Pembrolizumab (MK-3475) 200mg IV over 30 mins on D1 of 21-day cycles

- An unscheduled visit can occur at any time during the study. Source must be maintained for these unscheduled visits. The date for the visit and any data generated must be recorded on the appropriate CRF. Source documents for these unscheduled visits must also be maintained. In cases of aplasia, CBCs will be performed weekly and Bone marrow aspirates and biopsies will be performed every 3 months until recovery.

1: Hematology assessment includes complete blood count and differential blood count.

2: Chemistry assessment includes serum sodium, potassium, chloride, carbon dioxide, serum urea nitrogen, creatinine, calcium, glucose, alkaline phosphatase, AST, ALT, total bilirubin, total protein, albumin. Blood samples for LFTs must be collected and analyzed at local or central labs within 3 days prior to dosing. LFT results must be reviewed by the principal investigator (or designee) to meet dosing criteria specifications: $\leq 3 \times$ ULN for AST, ALT and $\leq 2 \times$ ULN for Total bilirubin unless liver metastases are present in which case LFT $\leq 5 \times$ ULN for AST, ALT and Total bilirubin $\leq 3.0 \times$ ULN) prior to dosing. If, during the course of treatment abnormal LFT values are detected, entinostat and Pembrolizumab (MK-3475) will not be administered. The subject should be evaluated and managed referring to the protocol, as clinically appropriate.

In addition, evaluation for pituitary function must be made prior to each infusion either by clinical history, TSH or both.

3: Pregnancy tests for females of childbearing potential. A female of childbearing potential is a sexually mature female who: 1) has not undergone a hysterectomy or bilateral oophorectomy; or 2) has not been naturally postmenopausal for at least 24 consecutive months (i.e., has had menses at any time in the preceding 24 consecutive months).

4: An additional safety assessment will be done before each maintenance dose.

5: Bone marrow assessment will be performed in patients at baseline (before cycle 1), after cycles 1 (entinostat alone) and then every 2 cycles of entinostat and Pembrolizumab (MK-3475) dose. At baseline, bone marrows will be sent for analysis of aspirate, biopsy, flow cytometry, iron stain, correlative studies, cytogenetics and FISH. FISH panel will include probes to identify 5q-, 7q-, trisomy 8, 20q-. Follow-up bone marrows will be analyzed for aspirate, biopsy, and flow cytometry. Cytogenetics will be sent after cycle 2, 4 and subsequent bone marrow studies.

Iron stains and FISH will be repeated at discretion of investigator.

6: Survival follow-up should be obtained monthly from time of study drug discontinuation or disease progression, whichever occurs first, for 6 months. Survival follow-up will be collected via telephone calls, patient medical records, or clinic visits.

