We will perform '3+3' classical dose escalation design to determine DLT. The first 3 patients will receive ENT at dose level 1 (DL1: 8mg on D1, 8 of 21-day cycles). pembrolizumab (MK-3475) will be added starting day 1 cycle 2 at the approved dose (200mg intravenously [IV] over 30 minutes on D1 of 21-day cycles) for 4 cycles. A safety committee that includes the study chair, the principal investigator from any study site that has enrolled a patient on the specific DL, as well as two sub-investigators from Yale will review safety data after enrollment of every 3 patients during the dose escalation phase. The committee will have the discretion to decide to enroll 3 more patients in the specific dose level even if no DLT occurred in the first 3 treated patients in that dose level if there are toxicity/safety concerns that did not qualify as DLT (maximum of 6 evaluable patients to be enrolled at any dose level). The committee can also decide to enroll patients at a lower dose level after the first 3 or after the first 6 patients enrolled in any dose level even if no or one DLT occurred at that dose level if there are toxicity/safety concerns that did not qualify as DLT. The following regarding enrollment in different dose levels will be considered guidance for the safety committee but can be modified in accordance of above: If no patient of the 3 patients treated with combined therapy at DL1 develops DLT, then dose level 2 (DL2) will be tested. DL2 will be with ENT at 8mg on D1, 8 and 15 and pembrolizumab (MK-3475) at 200mg IV on D1 of 21-day cycles. If 1 patient out of the 3 patients has DLT at DL1, we will expand cohort to 3 more patients and if 1 patient of the 6 patients has DLT (i.e. only 0/3 or 1/6), we will test next dose (DL2). If no patient of the 3 patients treated with combined therapy at DL2 develop DLT, then DL2 will be used for part 2 (expansion cohort). If 1 patient out of the 3 patients has DLT at DL2, we will expand cohort to 3 more patients and if 1 patient of the 6 patients has DLT (i.e. only 0/3 or 1/6), dose level 2 (DL2) will be used for part 2 (expansion cohort). If 2 patients or more of the 6 patients at DL2 experience DLT, DL1 will be used for expansion cohort. The cycle duration will be 21 days, the maximum number of treatment cycles of entinostat will be 18 cycles and for pembrolizumab (MK-3475) the maximum number of cycles will be 17. Cycle 2 to cycle 18, will have concurrent administration. In all the phases of the study, entinostat will be administered in clinic within 2 hours before administration of pembrolizumab (MK-3475). Entinostat will be stored at the pharmacy and it will not be given for the patient to take home.

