One of the HDACs studied in MDS is entinostat: an orally bioavailable, isotype-selective class 1-specific HDACi with long half-life (100 hours). A phase I clinical trial published in abstract form at Johns Hopkins University combined entinostat with a lower dose, prolonged administration schedules of azacitidine²². In this trial, patients were treated with SQ azacitidine for 10 days at different dose levels (30, 40, or 50mg/m²/day) and given oral entinostat (2, 4, 6, 8 mg/m²/dose) on days 3 and 10. Out of 31 enrolled patients, 13 had MDS, 4 had chronic myelomonocytic leukemia (CMML), and 14 had acute myeloid leukemia (AML). Patients were evaluable for response if they received 4 or more cycles of treatment. Of the 27 evaluable patients, 12 had responses (2 CR, 4 had partial responses [PR], and 6 bilineage hematologic improvement [HI]) according to the International Working Group [IWG] 2000 criteria. The 50mg/m²/day dose of azacitidine D1-10 and the entinostat 4 mg/m²/dose on D3 and D10 were subsequently studied in the randomized phase 2 ECOG1905 study versus azacitidine monotherapy at the same 50mg/m²/day dose D1-D10²³. Both arms achieved rates of trilineage hematologic normalization (32% for azacitidine monotherapy and 27% for combination) that were exceeded that of the historical control in which the standard regimen of azacitidine at 75mg/m²/day D1-7 was used (16% in CALBG9221 trial). While there was no survival advantage with the combination compared to azacitidine, this could be potentially related to pharmacologic antagonism caused by early administration of entinostat, a potent cell-cycle inhibitor with a long half-life of 4.5 days, in each cycle (day 3) which could have inhibited incorporation of azacitidine into DNA and subsequent cell cycling²³. These findings suggest that while entinostat has a modest activity in MDS, HMAs might not be the best choice

for combination-based regimen with entinostat. Exploration of alternative agents to combine with entinostat in the post-DNMTi failure setting might be a more rational approach.

Rationale for use of immune-check point inhibitors in MDS after DNMTi failure

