As can be seen from the table, the dose we proposed (4mg/m² weekly) has been widely used in other studies and has been well tolerated (see especially Hausschild et al, Gore et al and Batlevi et al) and therefore was chosen as the RP2D. This dose was already used in combination with azacitidine (a drug which has more myelosuppressive potential than pembrolizumab). This E1905 study was a randomized phase 2 study ([NCT00313586](#)) of 10 days of AZA (50 mg/m²/d) +/- entinostat (4 mg/m²) given on days 3 and 10 of each cycle and enrolled 149 patients with MDS and the combination was well tolerated ²³. Given that the entinostat manufacturer recommended the use of a flat dose of entinostat of 8 mg Po instead

of 4mg/m² based on a study that showed BSA-based dosing is not more accurate than fixed dosing⁴⁷.

PART 1:

The ENT monotherapy run-in part (cycle 1) will allow to study the changes in myeloid derived suppressor cells (MDSCs) at pre- and post- ENT treatment (the end of cycle 1) to dissect the effects of ENT monotherapy from those of the combined ENT/anti-PD1 therapy.

[figure not shown]

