We will perform '3+3' classical dose escalation design to determine dose limiting toxicity (DLT). The first 3 patients will receive ENT at dose level 1 (DL1: 8mg on D1, 8 of 21-day cycles). pembrolizumab (MK-3475) will be added starting day 1 cycle 2 at the approved dose of 200mg intravenously [IV] over 30 minutes on D1 of 21-day cycles) for 4 cycles (cycle 2-5). A safety committee that includes the study chair, the principal investigator from any study site that has enrolled a patient on the specific DL, as well as two sub-investigators from Yale will review safety data after enrollment of every 3 patients during the dose escalation phase. The committee will have the discretion to decide to enroll 3 more patients in the specific dose level even if no DLT occurred in the first 3 treated patients in that dose level if there are toxicity/safety concerns that did not qualify as DLT (maximum of 6 evaluable patients to be enrolled at any dose level). The committee can also decide to enroll patients at a lower dose level after the first 3 or after the first 6 patients enrolled in any dose level even if no or one DLT occurred at that dose level if there are toxicity/safety concerns that did not qualify as DLT. The following regarding enrollment in different dose levels will be considered guidance for the safety committee but can be modified in accordance of above: If no patient of the 3 patients treated with combined therapy at DL1 develops DLT, then dose level 2 (DL2) will be tested. For instance, DL2 will be with ENT at 8mg on D1, 8 and 15 and pembrolizumab (MK-3475) at 200mg IV on D1 of 21-day cycles. If 1 patient out of the 3 patients has DLT at DL1, we will expand cohort to 3 more patients and if 1 patient of the 6 patients has DLT (i.e. only 0/3 or 1/6), we will test next dose (DL2). If no patient of the 3 patients treated with combined therapy at DL2 develop DLT, then DL2 will be used for part 2 (expansion cohort). If 1 patient out of the 3 patients has DLT at DL2, we will expand cohort to 3 more patients and if 1 patient of the 6 patients has DLT (i.e. only 0/3 or 1/6), dose level 2 (DL2) will be used for part 2 (expansion cohort). If 2 or more patients of the 6 patients have DLT, DL1 will be used for expansion cohort. The cycle duration will be 21 days, the maximum number of treatment cycles of entinostat will be 18 cycles and for pembrolizumab (MK-3475) the maximum number of cycles will be 17. Cycle 2 to cycle 18, will have concurrent administration. In all the phases of the study, entinostat will be administered in clinic within 2 hours before administration of pembrolizumab (MK-3475). Entinostat will be stored at the pharmacy and it will not be given for the patient to take home.

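### The study calendar's Cycle 1 line gives entinostat on three days with no dose-level limit, while the synopsis, 5.1 and 13.1 imply two days at DL1: 24 mg against 16 mg in the run-in at the starting level

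*Combined protocol and SAP*

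**What the plan says.** Two places in Section 10 and three places outside it bear on entinostat in Cycle 1, the cycle without pembrolizumab.

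- **Section 10, notes under the calendar:** "Cycle1: Entinostat 8mg po on D1, 8 and 15, no Pembrolizumab (MK-3475". No dose level is named. Separate lines for DL1, DL2 and DL-1 follow.
- **Section 10, entinostat row of the table:** "Entinostat (depending on dose level", with marks at D1, D8 and D15 of each cycle.
- **Synopsis (Part 1), Section 5.1 and Section 13.1:** "The first 3 patients will receive ENT at dose level 1 (DL1: 8mg on D1, 8 of 21-day cycles". Each then says that pembrolizumab "will be added starting day 1 cycle 2".

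Section 5.1 gives the purpose of the run-in: it allows MDSC changes to be studied "to dissect the effects of ENT monotherapy from those of the combined ENT/anti-PD1 therapy".

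**The concern.** Entinostat schedule is the only thing that differs between the dose levels, and finding a tolerable one is the primary objective. The calendar is a document that sites dose from. If one site follows its Cycle 1 line and another follows Section 5.1, patients registered to the same level receive different amounts of an investigational drug, at the level where the trial starts.

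A second consequence concerns the correlative work. If DL1 patients take three doses in Cycle 1 and two in Cycle 2, the entinostat schedule changes in the same cycle that pembrolizumab begins. A change in MDSCs between those cycles could then come from either.

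**Working it through.** **Inputs.** Each dose is 8 mg at every level (dose tables in the synopsis and Section 5.1). Dosing days per 21-day cycle are D1 at DL-1; D1 and D8 at DL1; D1, D8 and D15 at DL2. The calendar's Cycle 1 line has three dosing days.

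**Formula.** Cycle 1 entinostat in mg = 8 × number of dosing days. The plan states no total per cycle, so there is no printed figure to reproduce first.

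| Level | Calendar's Cycle 1 line | Level's own schedule | Ratio | Change at Cycle 2 under the calendar line |
|---|---|---|---|---|
| DL1 | 8 × 3 = 24 mg | 8 × 2 = 16 mg | 24/16 = 1.5 | (16 − 24)/24 = −33% |
| DL-1 | 24 mg | 8 × 1 = 8 mg | 24/8 = 3.0 | (8 − 24)/24 = −67% |
| DL2 | 24 mg | 8 × 3 = 24 mg | 1.0 | 0 |

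The DL-1 row applies only if that backup level is opened and its schedule is meant to cover Cycle 1. Under each level's own schedule, nothing changes at Cycle 2.

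**Do the passages really differ?** The phrase *from Cycle 1* is not printed in Sections 5.1 or 13.1. It is an inference: the first patients are put on entinostat at DL1, and pembrolizumab is then added at Cycle 2 to a drug they are already taking. The calendar row, which ties the days to the dose level in each cycle, points the same way. So does Section 5.2, where the only change of level foreseen in the run-in is a reduction for entinostat toxicity. None of these passages describes a common three-dose run-in, and the Cycle 1 line does. The combined-cycle schedules agree everywhere.

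**How many patients the conflict covers.** Part 2 also includes the monotherapy cycle (Section 5.1), so expansion patients count. Replacements, and a restart of the expansion at a lower level under the toxicity rule, are left aside.

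- DL2 expanded: the DL1 cohort only, 3 to 6.
- DL1 expanded: 3 to 6, plus 15 = 18 to 21.
- DL-1 expanded (same condition as above): 3 to 6, plus 6, plus 15 = 24 to 27.

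**Minor item, separate from the above.** In Section 6.1.3, the hematologic dose-modification table refers to patients dosed on days 1, 8 and 21. No dose level has that schedule. The table is guidance and not mandatory.

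**The case against.** **A common run-in may be intended.** The dose-level tables define each level as entinostat plus pembrolizumab, and the calendar lists Cycle 1 apart from the levels. A uniform three-dose run-in is therefore a possible reading. The figures beside the run-in text in the synopsis and Section 5.1 are not shown in the copy reviewed and may state a schedule. This stands as a reason not to say which instruction is right. It does not make the printed passages agree: if a common run-in is meant, the synopsis, 5.1 and 13.1 omit it, and the calendar's own row conflicts with it.

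**Sites have other safeguards.** Registration returns treatment information to the site, dose decisions need sign-off through CTMS/IWRS, and investigators confer at least monthly. These may catch a discrepancy, but the documents do not say that any of them states the Cycle 1 schedule.

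**The MDSC consequence is limited.** DL2 patients have no change of dose. The comparison is exploratory. The planned mixed models (Section 13.4, Appendix J) look at change over time and name no contrast of Cycle 1 against the combination. Even with a constant schedule, a single-arm sequence mixes pembrolizumab with longer entinostat exposure. All of this stands. It narrows the point to DL1 and DL-1 patients, for whom a change of dose is added to a comparison that is already imperfect.

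**A reader might try to size the MDSC effect from drug remaining at the marrow.** The protocol gives two half-lives, "with long half-life (100 hours" and "a long half-life of 4.5 days", and draws marrow on D17 to D20 ("of first cycle, and then every 2 cycles [C3, 5, etc"). Assuming first-order decay at 100 hours, entinostat left at the Cycle 1 marrow relative to the C3 marrow at DL1 runs from about 2.0 to 5.5 under the calendar line and 0.6 to 1.6 under the DL1 schedule, depending on the days chosen in each cycle. Section 11 also gives a different marrow timing, after cycles 2 and 4, and no passage links remaining drug to MDSC level. The documents therefore support no such figure as an effect on an outcome.

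**Conclusion.** The contradiction is real and one text must change. At DL1 it amounts to 24 mg against 16 mg in Cycle 1, a factor of 1.5. At DL-1 it is 24 mg against 8 mg, on the two conditions given above. At DL2 there is none. The DL1 figure assumes that the dose-level schedule applies from the run-in, which the synopsis, 5.1 and 13.1 imply without stating.

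It matters first as a dosing instruction at the starting level that sites could read in two ways. For DL1 patients dosed by the calendar line, it also undermines the stated purpose of the run-in, because entinostat falls by one third as pembrolizumab starts; that consequence concerns an exploratory comparison only.

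A reader might infer that the MTD would be biased. The documents do not support that. Section 5.2 confines DLTs to the first two combined cycles, so Cycle 1 lies outside the window, and any indirect route from run-in dosing to the MTD would be speculation.

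**What to change.** - Reconcile the calendar's Cycle 1 line and entinostat row with the synopsis, Section 5.1 and Section 13.1. State one Cycle 1 entinostat schedule for each dose level, including DL-1 and the expansion cohort. The clinical team decides which instruction stands.
- Check the Cycle 1 dosing records of patients already treated.
- Use the entinostat dose actually given in Cycle 1 in the MDSC analysis, and report which patients had a change of schedule at Cycle 2.
- Separately, reconcile the reference to days 1, 8 and 21 in Section 6.1.3 with the defined dose levels.

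**Cost.** A wording change, either in the calendar or in the synopsis, 5.1 and 13.1 depending on what is decided, plus a small correction in 6.1.3 and a review of dosing records. Sample size and the DLT rules are untouched.

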Gore et al, Clin Cancer Research [3]	I	27 patients with refractory solid tumors and lymphomas	Part 1: Entinostat 2, 4, or 6 mg/m ² PO every 2 weeks Part 2: Entinostat 2 mg/m ² twice weekly for 3 of 4 weeks Part 3: Entinostat 4 or 5 mg/m ² weekly for 3 of 4 weeks	MTD: 6 mg/m² every other week or 4 mg/m² weekly for 3 weeks followed by 1 week of rest DLT: Hypophosphatemia and asthenia were dose limiting on the weekly and twice-weekly dosing schedules no dose-limiting toxicity on every other week schedule

Batlevi et al, Haematologica [4]	II	49 patients with relapsed /refractory Hodgkin lymphoma	Part 1: Entinostat 10 to 15 mg PO every 2 weeks (Days 1 and 15) of a 4-week cycle Part 2: Entinostat 15 mg Days 1, 8, and 15 of a 4-week cycle	Most frequent grade 3 and 4 AE: thrombocytopenia (63%), anemia (47%), neutropenia (41%), leukopenia (10%), hypokalemia (8%), and hypophosphatemia (6%). Does reduction/delays: 51% of patients
Solid malignancies				
Denis et al, JCO 2014 (abstract) [5]	I/	ER+ breast cancer or NSCLC	Cycle 1: All patients: Entinostat 10 mg PO on Day 1 under fed conditions and on Day 15 under fasted conditions or on Day 1 under fasted conditions and on Day 15 under fed conditions. Cycle2: Breast cancer: Entinostat 10 mg PO on Days 1 and 15 at least 2 hours after breakfast followed by a \geq 1-hour fast every 28 days + exemestane 25 mg QD PO NSCLC: Entinostat 10 mg PO on Days 1 and 15 at least 2 hours after breakfast followed by a \geq 1-hour fast every 28 days + erlotinib 150 mg QD PO	Entinostat was well tolerated with no unexpected toxicities Results only published in abstract form without many details provided
Hausschild et al, Melanoma Research [6]	II	28 patients with non-resectable metastatic melanoma	Arm A: Entinostat 3 mg Days 1 and 15 of 4-week cycle Arm B: 7 mg Days 1, 8, 15 of 4-week cycle	No treatment-related serious adverse events occurred. Toxicity was mild to moderate with nausea (39%) and hypophosphatemia (29%) as the most frequently reported events. occurrence of the most common adverse events was similar in both treatment arms

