METABOLISM AND NUTRITION DISORDERS			
Anorexia			Anorexia (Gr 3)
	Dehydration		Dehydration (Gr 2)
	Hyperglycemia		Hyperglycemia (Gr 2)
Hypoalbuminemia			Hypoalbuminemia (Gr 2)
	Hypocalcemia		Hypocalcemia (Gr 2)
	Hypokalemia		Hypokalemia (Gr 2)
	Hyponatremia		Hyponatremia (Gr 3)
Hypophosphatemia			Hypophosphatemia (Gr 3)

Adverse Events with Possible Relationship to MS-275 (SNDX-275, entinostat) (CTCAE 5.0 Term) [n= 221]			Specific Protocol Exceptions to Expedited Reporting (SPEER)
Likely (>20%)	Less Likely (<=20%)	Rare but Serious (<3%)	
MUSCULOSKELETAL AND CONNECTIVE TISSUE DISORDERS			
	Myalgia		Myalgia (Gr 2)
NERVOUS SYSTEM DISORDERS			
	Dysgeusia		Dysgeusia (Gr 2)
Headache			Headache (Gr 2)
RESPIRATORY, THORACIC AND MEDIASTINAL DISORDERS			
	Cough		Cough (Gr 2)
	Dyspnea		Dyspnea (Gr 3)
SKIN AND SUBCUTANEOUS TISSUE DISORDERS			
		Erythema multiforme	

¹This table will be updated as the toxicity profile of the agent is revised. Updates will be distributed to all Principal Investigators at the time of revision. The current version can be obtained by contacting [contact]. Your name, the name of the investigator, the protocol and the agent should be included in the e-mail.

²Infection includes all 75 sites of infection under the INFECTIONS AND INFESTATION SOC.

³Gastrointestinal hemorrhage includes Anal hemorrhage, Cecal hemorrhage, Colonic hemorrhage, Duodenal hemorrhage, Esophageal hemorrhage, Esophageal varices hemorrhage, Gastric hemorrhage, Hemorrhoidal hemorrhage, Ileal hemorrhage, Intra-abdominal hemorrhage, Jejunal hemorrhage, Lower gastrointestinal hemorrhage, Oral hemorrhage, Pancreatic hemorrhage, Rectal hemorrhage, Retroperitoneal hemorrhage, and Upper gastrointestinal hemorrhage under the GASTROINTESTINAL DISORDERS SOC.

Adverse events reported on MS-275 (SNDX-275, entinostat) trials, but for which there is insufficient evidence to suggest that there was a reasonable possibility that MS-275 (SNDX-275, entinostat) caused the adverse event:

BLOOD AND LYMPHATIC SYSTEM DISORDERS - Febrile neutropenia; Hemolysis; Leukocytosis

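### The scheduled chemistry panel does not require phosphate, although the protocol names hypophosphatemia as dose limiting on weekly entinostat; detection in the DLT window is therefore left to site discretion, with a probably small effect on the MTD

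*Combined protocol and SAP*

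**What the plan says.** **The panel.** Footnote 2 to the Study Calendar reads: "Chemistry assessment includes serum sodium, potassium, chloride, carbon dioxide, serum urea nitrogen, creatinine, calcium, glucose, alkaline phosphatase, AST, ALT, total bilirubin, total protein, albumin". That is 14 analytes. Alkaline phosphatase is an enzyme and gives no phosphate level. The calendar marks serum chemistry at screening and on D1, D8 and D15 of each cycle; the text above it sets a looser minimum: "CBC with differentials, serum chemistry and Liver function tests (LFTs) will be performed at least every 2 weeks". No other row or section schedules phosphate.

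**What the protocol expects of entinostat.** The table in section 5.1 reports hypophosphatemia in several studies:
- 27-patient phase I study in refractory solid tumors and lymphomas: "Hypophosphatemia and asthenia were dose limiting on the weekly and twice-weekly dosing schedules". Its weekly schedule was 3 weeks of every 4.
- Phase II melanoma study: "Toxicity was mild to moderate with nausea (39%) and hypophosphatemia (29%) as the most frequently reported events".
- Phase II Hodgkin lymphoma study, 10–15 mg doses: among the most frequent grade 3 and 4 events, "hypokalemia (8%), and hypophosphatemia (6%)".

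The entinostat risk list (section 7.1.1.1) has hypophosphatemia in the Likely (>20%) column, with the expedited-reporting exception "Hypophosphatemia (Gr 3)".

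**The schedule tested here.** "DL2 will be with ENT at 8mg on D1, 8 and 15" of a 21-day cycle. The next cycle's first dose falls on day 22, so dosing is weekly without a break.

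**The DLT rule.** Section 5.2 counts any grade 3 or 4 non-hematologic toxicity in the first two combined cycles, unless clearly unrelated to the study drugs. It excepts transient laboratory abnormalities that can be treated or that fall to grade 2 or less within 72 hours.

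**The concern.** The primary endpoint is the MTD, and it rests on DLT counts in cohorts of three to six patients. One event counted or not counted can change an escalation decision. Here the protocol identifies a laboratory toxicity that limited dosing on weekly entinostat, escalates to a weekly schedule without that study's rest week, and does not require the test that would reveal it.

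Hypophosphatemia is graded from a laboratory value or from the treatment it prompts, so without a required test the finding depends on local habit or on symptoms. In a multisite trial, the same abnormality could be a DLT at one site and go unrecorded at another. The 72-hour exception has the same weakness: it can be applied only to an abnormality that has been detected, and showing resolution needs a second value. Section 6 also ties dose changes to the grade of non-hematologic toxicity, and expedited reporting of hypophosphatemia depends on its grade. Separately from the MTD, patients could go without detection of an electrolyte loss that can be corrected.

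**Working it through.** **1. The plan's own figures.** For the expansion stop (section 5.3: two or more DLTs in the first six evaluable patients), with X ~ Bin(6, p) and q = 1 − p:

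P(stop) = 1 − q^6 − 6pq^5

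- p = .50: .891 (stated: at least .89)
- p = 1/3: .649 (stated: .65); p = .33 exactly gives .642

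The stated figures reproduce. They treat every DLT as observed.

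**2. Inputs for the effect of missed events.** The documents give no DLT rate for this combination and no rate of DLT-qualifying hypophosphatemia, so both are assumed:
- other DLTs: 15% per patient (assumption);
- countable hypophosphatemia, h: 1%, 2% or 5%, independent of the others (assumption). The only grade 3–4 rate in the documents is 6%, from 10–15 mg doses and before any 72-hour exemption; it is shown as an outer reference.

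**3. Formulas.**
- True DLT rate: p = 1 − (.85)(1 − h)
- 3+3 acceptance (0 of 3, or 1 of 3 followed by 0 of 3): q^3 + 3pq^5
- Expansion stop: as in step 1

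The h = 0 row is also what the rules see when every hypophosphatemia DLT is missed.

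| h | True p | 3+3 accepts | Expansion stops |
|---|---|---|---|
| 0 (none, all exempt, or all missed) | .150 | .814 | .224 |
| 1% | .1585 | .797 | .244 |
| 2% | .167 | .779 | .264 |
| 5% | .1925 | .725 | .326 |
| 6% (reference) | .201 | .706 | .347 |

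Example at h = 5%: q = .85 × .95 = .8075. Acceptance = .5265 + 3(.1925)(.3433) = .5265 + .1983 = .725. Stop = 1 − .2772 − 6(.1925)(.3433) = 1 − .2772 − .3965 = .326.

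**4. The other reading of acceptance.** Section 5.2 also requires at least six patients at the recommended dose. If acceptance means one or fewer DLTs in six, it is one minus the stop probability: .776 at h = 0, .756 at 1%, .736 at 2% and .674 at 5%. The size of the change is similar.

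**5. What the shift means.** If all countable cases were missed, the rules would act on the first row while the truth lay in a lower one. At h = 1–2% the loss is 2 to 4 percentage points in either rule. At 5% it is 9 points in acceptance (.814 − .725) and 10 in the stop (.326 − .224). If some sites test, the loss is smaller.

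**The case against.** The strongest reply is that the DLT definition already removes most of these events. Its exception covers laboratory abnormalities that can be treated or that resolve, and hypophosphatemia is usually correctable. Section 5.5 points the same way: drug-related grade 3–4 electrolyte abnormalities that need only replacement do not in general require stopping treatment. This stands, and it is the main reason the effect on the MTD is probably small. It does not remove the need for the test, since an unmeasured abnormality is neither treated nor shown to have resolved.

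The quoted rates also need care. The 29% in melanoma comes from a study with mild to moderate toxicity and no treatment-related serious adverse events; one of its arms, 7 mg on days 1, 8 and 15 of 4 weeks, is close to dose level 2. The 6% comes from doses above 8 mg. The phase I entry does not say at which weekly dose hypophosphatemia was limiting. Dose level 1, with two doses in 21 days, is less dense than that study's weekly schedule, so the point bears chiefly on dose level 2.

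A reader might infer that phosphate will never be measured. The documents do not support that: the footnote says what the assessment includes, the risk list alerts every site to hypophosphatemia, all adverse events must be reported, and unscheduled visits are allowed. The test is not required, which is different from not done.

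A reader might also assume countable rates of 10–20% and conclude that the MTD is seriously distorted. No figure in the documents supports rates that high.

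**Conclusion.** The point holds as a gap in required ascertainment. The panel does not call for phosphate, nothing else schedules it, and the protocol's own evidence marks hypophosphatemia as dose limiting on weekly entinostat and as likely. Detection in the DLT window would be uneven across sites, and neither the DLT definition nor its 72-hour exception can be applied to this event in a uniform way.

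A distorted MTD is not shown. The figures in the working rest on an assumed 15% rate of other DLTs, independence, and an assumed countable rate of 1–5%; they also take all such cases as missed, which is the worst case. The plan's stated stopping probabilities are correct as computed, and no sample-size, significance or power figure is affected. This is a cheap improvement to safety monitoring and to even DLT ascertainment, worth making before dose level 2 opens.

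**What to change.** Add serum phosphate to the analyte list in footnote 2 of the Study Calendar, at screening and at each scheduled D1, D8 and D15 chemistry. State that any grade 3–4 value is to be repeated in time to verify the existing 72-hour exception; scheduled weekly samples alone cannot do this. No dose, DLT criterion or decision rule needs to change.

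The cost is one more analyte on blood already drawn, an occasional repeat test, and slightly more recorded laboratory abnormalities.
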